7.2 Secondary Objectives

- To evaluate the effect of setanaxib on fatigue at Week 24
- To evaluate the effect of setanaxib on liver stiffness at Week 24
- To evaluate the effect of setanaxib on ALP, fatigue and liver stiffness at Week 24, where setanaxib doses are combined
- To evaluate the effect of setanaxib on pruritus at Week 24
- To evaluate the effect of setanaxib on markers of cholestasis at Week 24
- To evaluate the safety and tolerability of setanaxib over a 24-week treatment period

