10.7 Adverse Events

10.7.1 Treatment Period

The analysis of safety assessments over the **24-week treatment period** (Week 24 + 30 days) will be conducted:

- For patients enrolled under protocol version 5.0 or later who complete the 24-week treatment period, a Week 28 (EoT) visit will occur 30 days after the date and time of last dose of IMP. All safety data will be analyzed.
- For patients enrolled under protocol versions 1.0 to 4.0, treatment may have continued beyond Week 24. Regardless, the safety data will be cut at Week 28 (Week 24 + 30 days) to ensure a consistent safety follow-up period for all patients.

This approach enables the evaluation of the safety and tolerability of setanaxib over a 24-week treatment period, consistent with the study objectives.

The analysis of safety assessments over the **52-week treatment period** (Week 52 + 30 days) will also be conducted:

- Patients enrolled under protocol version 5.0 will contribute safety data up to Week 28 only. All safety data will be analyzed.
- For patients enrolled under protocol versions 1.0 to 4.0 who complete the 52-week treatment period and do not enter the extension phase, a Week 56 (EoT) visit will occur 30 days after the date and time of last dose of IMP. All safety data will be analyzed.
- For patients enrolled under protocol versions 1.0 to 4.0 who entered the extension phase, the safety data will be cut at Week 56 (Week 52 + 30 days) to ensure a consistent safety follow-up period for all patients.

This approach enables the evaluation of the safety and tolerability of setanaxib over the whole randomized treatment period and provides longer-term safety information. This approach will be applied to other safety endpoints.

Note: For the analysis of study drug exposure and compliance (Section 12.3.3), the last dose of IMP in the 24-week treatment period will be cut at week 24, and the last dose in the 52-week treatment period (for subjects who received more than 24 weeks of treatment) will be cut at week 52. "+ 30 days" will not be considered in the drug exposure and compliance.

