objectives, the SS will be used to analyze safety endpoints and assessments related to safety over two treatment periods, as defined in Section 10.7.1. PK analysis will be presented using the PKS.

For information on the control of overall Type 1 error rate in the primary endpoint refer to Section 12.5.1. Formal statistical testing will be conducted for the primary endpoint of change in ALP, secondary endpoint of fatigue (based on PROMIS short form and PBC40 questionnaires) and change in liver stiffness.

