Evaluation of drug-induced serious hepatotoxicity (eDISH) analysis will be conducted in order to explore potential liver toxicity signals by treatment group. A eDISH plot will be produced, which will display for each subject during the treatment period the maximal total ALT/AST value (expressed as a multiple of the ULN) against the maximal Total Bilirubin value (expressed multiple of the ULN) to identify possible values above Hy's law range. The plot will be produced using the SS and treatment period of 52 weeks (Section 10.7.1) and will display the maximal on-treatment value of ALT/AST and total bilirubin.

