12.6.5 Vital Signs

Observed values and change from baseline in vital signs will be summarized descriptively by scheduled visit and treatment group using the SS and treatment period of 52 weeks. Shift plots of baseline as compared to highest and lowest on treatment value by treatment group will be presented. Vital sign parameters to be summarized descriptively are pulse rate, systolic blood pressure (SBP), and diastolic blood pressure (DBP). By-subject listings of all the vital signs will also be provided. Body temperature will be listed only.

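### The eDISH liver plot is specified only for the 52-week period, so no eDISH display matches the 24-week safety objective, and its per-subject maxima come from windows of up to 198 or up to 394 days.

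*SAP*

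**What the plan says.** The safety objective in SAP 7.2 is "To evaluate the safety and tolerability of setanaxib over a 24-week treatment period", and protocol 2.2 sets the same duration. SAP 12.0 gives a general rule: "the SS will be used to analyze safety endpoints and assessments related to safety over two treatment periods, as defined in Section 10.7.1" (SS is the safety analysis set).

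SAP 10.7.1 defines the two periods.

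- **24-week period.** For patients enrolled under versions 1.0 to 4.0, "the safety data will be cut at Week 28 (Week 24 + 30 days) to ensure a consistent safety follow-up period for all patients".
- **52-week period.** "Patients enrolled under protocol version 5.0 will contribute safety data up to Week 28 only". For earlier patients who entered the extension, "the safety data will be cut at Week 56 (Week 52 + 30 days) to ensure a consistent safety follow-up period for all patients". Earlier patients who completed 52 weeks without entering it are followed to a Week 56 visit.

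SAP 12.6.4 specifies the eDISH plot, which takes each subject's maximum ALT/AST and maximum total bilirubin: "The plot will be produced using the SS and treatment period of 52 weeks". No 24-week version is mentioned. SAP 12.6.5 summarises vital signs by visit "using the SS and treatment period of 52 weeks". It then adds shift plots from baseline to the highest and lowest values without naming a period for them. In SAP 12.6.6, the corresponding ECG shift plots and the QTc outlier tables are planned for both periods.

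**The concern.** A maximum can only rise, or stay the same, as the window lengthens. A display of maxima in which some patients can be observed about twice as long as others mixes length of observation with whatever the drug does. The 24-week cut in SAP 10.7.1 was written to avoid this, but the eDISH plot does not use it.

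This matters more for eDISH than for most outputs because it is the only planned display by arm that shows transaminases and bilirubin together. The suspected-DILI proportions in SAP 12.6.3 count each test separately, the worst-grade shifts are per parameter, and Hy's law cases are only flagged in listings. The two maxima on an eDISH plot need not occur on the same day, so a longer window also gives unrelated peaks more chance to pair. Protocol 1.1.4 reports 4 SAEs of elevated liver tests, considered possibly related to the investigational product, at the August 2023 data cutoff. Readers will therefore look closely at the liver display.

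**Working it through.** The plan states no figure for this point, so there is none to reproduce. The check compares periods, then window lengths.

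**Step 1. Period named for each safety output (SAP section).**

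- Treatment-emergent adverse events (12.6.1): both.
- Worst-CTCAE-grade laboratory shifts (12.6.3): both.
- Suspected-DILI proportions for ALT/AST, bilirubin and INR (12.6.3): both.
- ECG highest/lowest shift plots and QTc outlier tables (12.6.6): both.
- eDISH plot of maxima (12.6.4): 52 weeks only.
- Vital-sign highest/lowest shift plots (12.6.5): none stated; the section's only named period is 52 weeks.
- Vital-sign summaries (12.6.5), ECG categories and physical examinations (12.6.6): 52 weeks only, but tabulated by visit.

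The by-visit tables contain no peaks, and a 24-week cut would leave their rows up to Week 24 unchanged. That leaves eDISH and, by inference, the vital-sign shift plots.

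**Step 2. Maximum windows, from SAP 10.7.1.**

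- Week 24 + 30 days: 24 × 7 + 30 = 198 days.
- Week 52 + 30 days: 52 × 7 + 30 = 394 days.
- Ratio: 394 / 198 = 1.99.

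These are ceilings. The special note in protocol 3.1 tells patients already past Week 24 to stop treatment as soon as possible, so many earlier patients will fall between the two values.

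**Step 3. Illustration of what a longer window does to a maximum.** Assume, without support from the documents, a constant hazard of crossing a threshold. If p is the crossing probability over 198 days, the probability over 394 days is 1 − (1 − p)^(394/198).

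- p = 2% becomes 3.9%.
- p = 5% becomes 9.7%.
- p = 10% becomes 18.9%.
- p = 20% becomes 35.9%.

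These compare patients with the full long window to patients with the short one. They are not differences between arms.

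**Step 4. Between-arm effect.** If two arms have shares f1 and f2 of patients with the full long window, the spurious difference is (f1 − f2) × (p394 − p198). The documents do not give the shares, so the following are assumptions.

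- Equal shares: zero.
- 40% versus 20%: 0.4, 0.9, 1.8 and 3.2 percentage points for p = 2%, 5%, 10% and 20%.
- 50% versus 20%: 0.6, 1.4, 2.7 and 4.8 percentage points.

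For example, with p = 10% and 40% versus 20%: 0.2 × (18.91% − 10%) = 1.8 points.

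**The case against.** The strongest reply is that the 24-week safety question is well covered without eDISH. The outputs marked as both periods in the working include ALT/AST and bilirubin thresholds from the same tests that eDISH plots. This stands. A reader might infer that 24-week safety is answered only through peaks over unequal follow-up; the documents do not support that.

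Second, randomization is 1:1:1 and SAP 8.2 says version 5.0 did not change it, so protocol version should be balanced between arms in expectation. SAP 12.5.4 also expects few subjects beyond Week 24. This stands too, with two limits. Stratification is by screening ALP only and arms have about 22 patients, so chance imbalance is possible. Discontinuation happens after randomization, and since liver findings can lead to it, follow-up length may depend on liver tolerability.

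Third, eDISH is exploratory and the longer period is the more cautious choice. A 52-week maximum cannot be lower than the 24-week one, so no early signal is lost, and SAP 10.7.1 justifies the period as giving longer-term safety information. This is a good reason to keep the 52-week plot, but not for having no 24-week one: the plot cannot show whether a high point arose before or after Week 28.

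Fourth, pairing maxima from different days is part of the plot as specified. A Week 28 cut would not make them concurrent, and the Hy's law flag in SAP 12.6.3 already requires concurrence. Correct: the cut shortens the window but does not remove this feature.

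Finally, SAP 12.6.5 does not actually give the vital-sign shift plots a period. That is why this part of the point is conditional.

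**Conclusion.** The point holds in a limited form. The eDISH plot is planned only over the 52-week period, where maximum windows differ by protocol version (198 versus 394 days). No eDISH display therefore corresponds to the 24-week objective, follows the two-period rule in SAP 12.0, or can be set beside the 24-week adverse-event and suspected-DILI tables. It does have 52-week counterparts. The vital-sign shift plots share the problem if 52 weeks is their intended period.

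A reader might go further and conclude that physical examinations, ECG categories and the main vital-sign summaries are distorted, or that the arm comparison is biased. The first does not follow, because those tables are by visit; for them the only issue is consistency with SAP 12.0. The second is not shown: expected imbalance in protocol version is zero, and the 0.4 to 4.8 point range in the working rests wholly on assumed hazards and shares. The actual size cannot be computed from the documents. This is a minor, easily corrected gap in the planned outputs.

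**What to change.** In SAP 12.6.4, add an eDISH plot cut at Week 24 + 30 days as defined in SAP 10.7.1. In SAP 12.6.5, state the period for the highest/lowest shift plots and produce them for both periods, as is already planned for ECG. Keep the 52-week versions alongside; there is no need to demote them. Reconcile SAP 12.6.4 to 12.6.6 with 12.0, either by naming both periods or by stating which outputs are exceptions and why. Also clarify which period is meant by the closing remark of SAP 10.7.1 that the approach extends to other safety endpoints, since it follows the descriptions of both.

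The cost is a re-run of planned programs with a cut that already exists, giving a few more outputs. No new data are needed and no longer-term information is lost. The cut equalises the maximum window only; actual follow-up will still vary with early discontinuation.

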12.6.5 Vital Signs

Observed values and change from baseline in vital signs will be summarized descriptively by scheduled visit and treatment group using the SS and treatment period of 52 weeks. Shift plots of baseline as compared to highest and lowest on treatment value by treatment group will be presented. Vital sign parameters to be summarized descriptively are pulse rate, systolic blood pressure (SBP), and diastolic blood pressure (DBP). By-subject listings of all the vital signs will also be provided. Body temperature will be listed only.

12.6.6 Physical Examinations, ECGs, and Other Observations Related to Safety

ECGs will be read centrally and ECG mean Heart Rate (HR), RR interval, PR Interval, QRS Duration, QT interval, QTcB interval and QTcF interval will be collected and summarized. In the Extension Phase, ECG may be read locally and HR, PR interval, RR interval, QRS interval, QT interval and QTcF interval will be listed. ECGs will be presented by the category normal, abnormal, unevaluable, and unknown for each assessment time point in the safety analysis, over the treatment period of 52 weeks. Shift plots of baseline as compared to highest and lowest on treatment value by treatment group will be presented for both treatment periods defined in Section 10.7.1. A listing of subjects ECG data will be provided.

QTc outliers are defined as QTc values following dosing that are greater than 450 msec or are increases from baseline greater than 30 msec. QTc outliers will be highlighted in the data listings, with subjects meeting the criteria at any time point listed separately. Outliers will be summarized using separate shift tables for each treatment period defined in Section 10.7for the following categories:

Version Date: 27-June-2024 Sponsor: Calliditas Therapeutics Suisse SA

Protocol No: GSN000350

Values ≤450 msec, >450-480 msec, >480-500 msec, >500 msec at baseline versus values ≤450 msec >450-480 msec, >480-500 msec, >500 msec post-dose

• Values ≤450 msec, >450-480 msec, >480-500 msec, >500 msec at baseline versus increase from baseline of ≤30 msec, >30-60 msec, >60-90 msec or >90msec post-dose

A summary of physical examination findings will be presented for each scheduled visits, showing the proportion of subjects with "Normal" and "Abnormal" physical examinations. The number of abnormal, clinically significant and not clinically significant assessments will be tabulated by scheduled visit using the SS and treatment period of 52 weeks. All physical examination findings will be provided in listings.

The Child-Pugh score and Child-Pugh classification of Severity of Cirrhosis as collected on the CRF page will be listed for all scheduled visits with flags to indicate in the value is treatment for each treatment periods defined in Section 10.7.1. The individual components required to calculate the Child-Pugh score and class will also be listed).

12.6.7 Liver Biopsy and Liver Histology

For qualifying subjects in the SS, the absolute and change from baseline in the Nakamuna total score and fibrosis subscore at Week 52 will be summarized. A listing for the historical liver biopsy and liver biopsy data will be provided.

12.7 Pharmacokinetics Analyses

Blood samples will be collected for measurements of plasma concentrations of setanaxib and its metabolite GKT138184 during the Main Part of the study. Samples will be collected pre-dose at Week 6, Week 24 and (under protocol versions 1.0 to 4.0) also Week 52. The PK analysis set will be used for PK analysis.

Plasma concentrations of setanaxib and GKT138184, along with blood sampling dates and actual blood sampling time relative to previous dosing time, will be listed by subject, dose group, actual treatment (can change within subject), by formulation; can change within subject] and nominal sampling time. Samples with time deviation from nominal time will be identified and listed. Plasma setanaxib and GK138184 concentrations below the quantifiable limit (BQL) will be set to ½ the lower limit of quantification (LLOQ) in the computation of mean concentration values.

Descriptive statistics (number of subjects, arithmetic mean, geometric mean, standard deviation, coefficient of variation for geometric mean, median, Q1, Q3, minimum, and maximum) will summarize the plasma concentrations of both setanaxib and GKT138184 at pre-dose Week 4, pre-dose Week 24 and, where relevant, pre-dose Week 52, by actual treatment (may change within subject). If 50% of the subjects at a given time point have values BQL then the descriptive statistics will not be presented and will instead display as BQL for the mean and minimum, with the exception of maximum all other statistics will be missing. Plasma setanaxib and GKT138184 concentrations (dose normalized as appropriate) vs study visit will be plotted as a box plot, by actual treatment (may change within subject) with corresponding sample sizes.

12.8 Data Collected Under Protocol Version 1.0

The following assessments will be collected under protocol version 1.0 and will not be included in the primary or final analysis. Listings will be produced for all subjects with data collected for these assessments:

- 5-D Itch Scale
- Pruritus-Visual Analogue Scale.

14.0 Glossary of Abbreviations

Glossary of Abbreviatio	ns:		
AE	Adverse Event		
AESI	Adverse Event of Special Interest		
ALP	Alkaline Phosphatase		
ALT	Alanine Aminotransferase		
AMA	Antimitochondrial Antibodies		
ANCOVA	Analysis of Covariance		
AST	Aspartate Aminotransferase		
ATC	Anatomic Therapeutic Classification		
ВМІ	Body Mass Index		
BQL	Below Quantifiable Limit		
C3M	A Peptide of Helical Collagen Type III Degradation		
CI	Confidence Interval		
СМН	Cochran Mantel Haenszel		
CONSORT	Consolidated Standards of Reporting Trials		
CRF	Case Report Form		
CTCAE	Common Terminology Criteria for Adverse Events		
DBP	Diastolic Blood Pressure		
DILI	Drug-Induced Liver Injury		
ECG	Electrocardiogram		
eDISH	Evaluation of Drug-Induced Serious Hepatotoxicity		
EAS	Extension Safety Analysis Set		
ELF	Enhanced Liver Fibrosis		
ENRL	All Enrolled Analysis Set		
EoT	End of Treatment		
EQ-5D	EuroQol 5-Dimension Utility Index		
ES	Extension Analysis Set		
FAS	Full Analysis Set		
FGF	Fibroblast Growth Factor		
GGT	Gamma Glutamyl Transpeptidase		
GM	Geometric Mean		
HR	Heart Rate		
hsCRP	High Sensitivity C-reactive Protein		
ICH	International Council for Harmonization		
IDMC	Independent Data Monitoring Committee		

Sponsor: Calliditas Therapeutics Suisse SA

Glossary of Abbreviation	ns:		
IgM	Immunoglobulin M		
IMP	Investigational Medicinal Product		
INR	International Normalized Ratio		
IXRS	Interactive Web Response System		
LLOQ	Lower Limit of Quantification		
LOCF	Last Observation Carried Forward		
LS	Least Squares		
MAR	Missing At Random		
MCMC	Markov Chain Monte Carlo		
MedDRA	Medical Dictionary for Regulatory Activities		
MELD	Model for End Stage Liver Disease		
MMRM	Mixed Model Repeated Measures		
MRE	Magnetic Resonance Elastography		
N/A	Not Applicable		
OCA	Obeticholic Acid		
PBC	Primary Biliary Cholangitis		
PIIINP	Amino Terminal Propeptide of Type III Procollagen		
PGIC	Patient's Global Impression of Change		
PGIS	Patient's Global Impression of Severity		
PK	Pharmacokinetic(s)		
PKS	PK Analysis Set		
PPS	Per Protocol Analysis Set		
PRO	Patient Reported Outcome		
PRO-C3	Released N-terminal Propeptide of Type III Collagen		
PROMIS	Patient-Reported Outcomes Measurement Information System		
PSO	ICON System of Record		
PT	Preferred Term		
RBC	Red Blood Cell		
SAP	Statistical Analysis Plan		
SAE	Serious Adverse Event		
SBP	Systolic Blood Pressure		
SD	Standard Deviation		
sDILI	Suspected drug induced liver injury		
SE	Standard Error		
SI	Système International		
SOC	System Organ Class		

Version Date: 27-June-2024

Sponsor: Calliditas Therapeutics Suisse SA

Glossary of Abbreviations:		
SS	Safety Analysis Set	
TEAE	Treatment-Emergent Adverse Event	
TIMP-1	Tissue Inhibitor of Metalloproteinase 1	
UDCA	Ursodeoxycholic Acid	
ULN	Upper limit of Normal	
WBC	White Blood Cell	
WI-NRS	Worst Itch Numerical Rating Scale	
WHODRUG	World Health Organization Drug Dictionary	

Sponsor: Calliditas Therapeutics Suisse SA

Protocol No: GSN000350

Appendix

Appendix 1: Handling of Partial Adverse Event Dates

In order to assign an AE with partial dates as treatment emergent in the Main Part and Extension Phase the following imputation rules will be used.

Table 9: Handling of Partial AE dates (D = Day, M = Month, Y=Year)

Date of Interest	Missing	Condition	Imputation
AE start date	D	M and Y is the same as M and Y of first dose of IMP	Date of first dose of IMP
		Y is prior to Y of first dose of IMP	Last day of the month
		Y is the same as Y of first dose of IMP, M is prior to M of first dose of IMP	Last day of the month
		M and/or Y is after first dose of IMP	First day of the month
	D, M	Y is the same as the Y of first dose of IMP	Date of first dose of IMP
		Y is prior to Y of first dose of IMP	Use 31st of December
		Y is after Y of first dose of IMP	Use 1 st of January
	М	Treat day as missing and use imputation rules for D and M as missing	See D, M imputation rules
	D, M, Y	None-date is completely missing	Date of first dose of IMP
AE End Date	D	M and Y same as date of last dose of IMP	Date of last dose of IMP
		M and Y not the same as date of last dose of IMP/date of last dose of IMP is missing	Set to the last day of the month, or the end of study/death date whichever is earliest
	D, M	Y is the same as last dose of IMP	Date of last dose of IMP
		Y is not the same as date of last dose of IMP/date of last dose of IMP is missing	Set to 31st of Dec, or the end of study/death date whichever is earliest
	М	Treat day as missing and use imputation rules for D and M as missing	See D, M imputation rules
	D, M, Y	None	No imputation, assume Ongoing

If the above imputation rules result in illogical dates adjust accordingly. If any estimated AE start date is after a complete/imputed AE end date, set the AE start date to be the first day in the AE end date month. If any estimated AE end date is prior to a complete/imputed AE start date set to be the last day of the AE start date month. Imputed values will not be displayed in listings.

Sponsor: Calliditas Therapeutics Suisse SA

Protocol No: GSN000350

Appendix 2: Handling of Partial Medications Dates

In order to assign medications as either prior and/or concomitant the following rules will be used.

Table 10: Handling of Partial Medication dates (D = Day, M = Month, Y=Year)

Date of Interest	Missing	Condition	Imputation
Medication start date	D	M and Y is the same as M and Y of first dose of IMP	Date of first dose of IMP
		M and/or Y is not the same as the first dose of IMP	First day of the month
	D, M	Y is the same as the Y of first dose of IMP	Date of first dose of IMP
		Y is not the same as first dose of IMP	Use 1 st of January
	М	Treat day as missing and use imputation rules for D and M as missing	See D, M imputation rules
	D, M, Y	None-date is completely missing	Assume prior and concomitant. Impute as the last day prior to the first dose of IMP.
Medication End Date	nd D	M and Y same as date of last dose of IMP	Date of last dose of IMP
Date		M and Y not the same as date of last dose of IMP/date of last dose of IMP is missing	Set to the last day of the month, or the end of study/death date whichever is earliest
	D, M	Y is the same as last dose of IMP	Date of last dose of IMP
		Y is not the same as date of last dose of IMP/date of last dose of IMP is missing	Set to the 31st of Dec, or the end of study/death date whichever is earliest
	М	Treat day as missing and use imputation rules for D and M as missing	See D, M imputation rules
	D, M, Y	None	No imputation, assume Ongoing

If the above imputation rules result in illogical dates adjust accordingly. If any estimated medication start date is after a complete/imputed medication end date, set the medication start date to be the first day in the medication end date month. If any estimated medication end date is prior to a complete/imputed medication start date set to be the last day of the medication start date month. Imputed values will not be displayed in listings. For PBC medications collected on the concomitant medication page of the CRF with missing dates that are identified as impacting efficacy through medical review, the above rules will be used to impute partial dates and all assessments collected past the imputed partial dates will be seen as assessments collected while on rescue medication.

Sponsor: Calliditas Therapeutics Suisse SA

Protocol No: GSN000350

Appendix 3: PROMIS-Short Form-Fatigue 7b Daily Scoring Tables Refer to HealthMeasures (2019) for further detail.

Fatigue 7b Daily – Adult v1.0			
Short Form Conversion Table			
Raw Score	T-score	SE*	
7	31.0	4.9	
8	36.3	3.5	
9	39.4	3.0	
10	41.6	2.7	
11	43.5	2.5	
12	45.2	2.4	
13	46.7	2.4	
14	48.1	2.3	
15	49.5	2.3	
16	50.9	2.3	
17	52.2	2.3	
18	53.6	2.4	
19	54.9	2.4	
20	56.2	2.4	
21	57.6	2.4	
22	58.9	2.4	
23	60.3	2.4	
24	61.7	2.4	
25	63.0	2.4	
26	64.4	2.4	
27	65.7	2.4	
28	67.2	2.4	
29	68.6	2.4	
30	70.2	2.4	
31	71.8	2.5	
32	73.6	2.6	
33	75.6	2.9	
34	78.1	3.2	
35	81.4	3.6	

^{*}SE = Standard Error on T-score metric

Version Date: 27-June-2024 Sponsor: Calliditas Therapeutics Suisse SA

Adult v1.0 - Depression 4a Short Form Conversion Table

T-score

41.0

49.0

51.8

53.9

55.7

57.3

58.9

60.5

Raw Summed

Score

5

6

8

9

10

11

Protocol No: GSN000350

SE*

6.2

3.2

2.7

2.4 2.3

2.3

2.3

2.3

